11.2.5. Safety/Reactogenicity

- For the analyses of solicited symptoms, missing or non-evaluable measurements will not be replaced. Therefore the analyses of the solicited symptoms based on the TVC will include only subjects with documented safety data (i.e. symptom screen completed).
- For the analyses of unsolicited adverse events/concomitant medication, all vaccinated subjects will be considered and subjects who did not report an event will be considered as subjects without an event.
- The maximum intensity of local injection site redness/swelling will be scored at GSK Biologicals as follows:

0	:	Absent
1	:	≤ 20 mm
2	:	>20 and ≤ 50 mm
3	:	> 50 mm

- The maximum intensity of fever will be scored at GSK Biologicals as follows:

Axillary	
0	: $< 37.5^{\circ}\text{C}$
1	: $\geq 37.5^{\circ}\text{C}$ and $\leq 38.0^{\circ}\text{C}$
2	: $> 38.0^{\circ}\text{C}$ and $\leq 39.0^{\circ}\text{C}$
3	: $> 39.0^{\circ}\text{C}$

Note that for all tables described in this section, the way the percentage of subjects will be derived will depend on the event analysed (see table below for details). As a result, the N value may differ from one table to another.

Event	N used for deriving % per subject for Vaccination phase
Solicited general symptom	All subjects with at least one solicited general symptom documented as either present or absent (i.e., symptom screen completed)
Solicited local symptom	All subjects with at least one solicited local symptom documented as either present or absent (i.e., symptom screen completed)
Unsolicited symptom	All subjects with study vaccine administered
Concomitant medication	All subjects with study vaccine administered

11.2.6. Management of missing data

Demography:

- For a given subject and a given demographic variable, missing measurements will not be replaced.

Immunogenicity:

- For a given subject and a given immunogenicity measurement time point, missing or non-evaluable measurements will not be replaced.

Reactogenicity and safety:

- Subjects who missed reporting symptoms (solicited/unsolicited or concomitant medications) will be treated as subjects without symptoms (solicited/unsolicited or concomitant medications, respectively).

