10.5. Derived and transformed data

- A seronegative subject is a subject with anti-HBs antibody concentration below the assay cut-off (< 6.2 mIU/ml).
- A seropositive subject is a subject with anti-HBs antibody concentrations above the assay cut-off (≥ 6.2 mIU/ml).
- A seroprotected subject is a subject with anti-HBs antibody concentrations above the protection level (≥ 10 mIU/ml).
- Anamnestic response to the single challenge dose is defined as:
 - At least (i.e. greater than or equal to) 4-fold rise in post-vaccination anti-HBs antibody concentrations in subjects seropositive at the pre-vaccination time point.
 - Post-vaccination, anti-HBs antibody concentrations ≥ 10 mIU/ml in subjects seronegative at the pre-vaccination time point.

- The Geometric mean antibody concentrations (GMCs) calculations will be performed by taking the anti-log of the mean of the \log_{10} concentration transformations. All subjects will be considered. Subjects whose antibody concentrations are below the cut-off of the assay will be given an arbitrary value of half the cut-off for the purpose of GMC calculation. Note that as per assay specification, results between the assay cut-off of 6.2 mIU/ml and 7.65 mIU/ml (= Lower limit of Quantification) will be quantified as 6.2 mIU/ml.
- For a given subject and a given immunogenicity measurement, missing or non-evaluable measurements will not be replaced. Therefore, an analysis will exclude subjects with missing or non-evaluable measurements.

Safety/Reactogenicity

- For the analyses of solicited symptoms, missing or non-evaluable measurements will not be replaced. Therefore the analyses of the solicited symptoms based on the TVC will include only subjects with documented safety data (i.e. symptom screen completed).
- For the analyses of unsolicited adverse events/concomitant medication, all vaccinated subjects will be considered and subjects who did not report an event will be considered as subjects without an event.

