9. CHANGES FROM PLANNED ANALYSES

The major changes from the protocol are,

- According-to-protocol cohort for analyses of antibody persistence defined in the protocol for the analysis of antibody persistence was removed from the SAP to reduce the number of cohorts used in the analysis. The analysis of persistence and response to challenge dose will be performed on the According-to-protocol cohort for analyses of immunogenicity. This change will not have significant impact on the analysis of persistence as no major difference in number of subjects expected between the ATP cohort for analysis of Immunogenicity and ATP cohort for analyses of antibody persistence.

Other changes include,

- The analysis for persistence and response to challenge dose is harmonized with respect to the cut-offs to consider.
 - The analysis to summarize the number and percentage of subjects between >10 mIU/mL and < 100 mIU/mL planned in the protocol was removed to be consistent with the endpoints of the study.
 - The analysis to summarize the post challenge dose response and anamnestic response stratified by the pre-challenge dose concentrations will be performed by considering the categories < 6.2 mIU/ml, ≥ 6.2 mIU/ml - < 10 mIU/ml, and ≥ 10 mIU/ml at pre-challenge dose time point.
- All the analysis of solicited and/or unsolicited adverse events will be performed for any, grade 3, by relationship to vaccination, and requiring medical attention to be consistent with the presentation of the adverse events summary.

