HBV Group= Subjects who previously received 4 doses of Infanrix hexa in first two years of life and received a challenge dose of HBV vaccine in this study

N = number of subjects in group included in the considered cohort

n/% = number/percentage of subjects receiving the specified total number of doses

Template 16 Compliance in returning symptom information (Total vaccinated cohort)

Group	Number of doses	Doses NOT according to protocol	Number of general SS	Compliance % general SS	Number of local SS	Compliance % local SS
HBV Group						

HBV Group= Subjects who previously received 4 doses of Infanrix hexa in first two years of life and received a challenge dose of HBV vaccine in this study

SS = Symptom screens/sheets used for the collection of local and general solicited AEs

Compliance % = (number of doses with symptom screen/sheet return / number of administered doses) X 100

Template 17 Percentage of subjects reporting either solicited symptoms or unsolicited adverse events during the 4-day (Days 0-3) post-vaccination period (Total vaccinated cohort)

Group	Any symptom			General symptoms			Local symptoms					
	N	N	%	95% CI	N	n	%	95% CI	N	n	%	95% CI
HBV Group												

HBV Group= Subjects who previously received 4 doses of Infanrix hexa in first two years of life and received a challenge dose of HBV vaccine in this study

N = number of subjects with administered dose

n/% = number/percentage of subjects presenting at least one type of symptom whatever the study vaccine administered

95%CI = Exact 95% confidence interval; LL = lower limit, UL = upper limit

Template 18 Percentage of subjects reporting solicited local symptoms during the 4-day (Days 0-3) post-vaccination period (Total vaccinated cohort)

Symptom	Type	HBV Group					95 % CI	
		N	n	%	LL	UL		
Pain	All							
	Grade 3							
	Medical advice							
Redness	All							
	> 50 mm							
	Medical advice							
Swelling	All							
	> 50 mm							
	Medical advice							

HBV Group= Subjects who previously received 4 doses of Infanrix hexa in first two years of life and received a challenge dose of HBV vaccine in this study

N = number of subjects with documented dose

n/% = number/percentage of subjects reporting the symptom at least once

95%CI = Exact 95% confidence interval; LL = lower limit, UL = upper limit

Grade 3 For Pain: severe: Significant pain at rest. Prevented normal everyday activities

For Redness/Swelling: > 50mm

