White - Caucasian / European Heritage, n (%)	
White - Arabic / North African Heritage, n (%)	

HBV Group= Subjects who previously received 4 doses of Infanrix hexa in first two years of life and received a challenge dose of HBV vaccine in this study

SD - Standard Deviation

N - Total number of subjects enrolled in the study

n (%) - Number (percentage) of subjects in a given category

Template 26 Solicited and Unsolicited symptoms experienced by at least 5 % of subjects classified by MedDRA Primary System Organ Class and Preferred Term within the 31-day (Days 0-30) post-vaccination - SAE excluded (Total Vaccinated cohort)

			HBV Group N = XXX		95% CI	
Primary System Organ Class (CODE)	Preferred Term (CODE)	n*	n	%	LL	UL
At least one symptom						
Blood and lymphatic system disorders (10005329)	Leukocytosis (10024378)					
Cardiac disorders (10007541)	Angina unstable (10002388)					
	Mitral valve disease (10061532)					
	Myocardial infarction (10028596)					
Respiratory, thoracic and mediastinal disorders (10038738)	Pleural effusion (10035598)					
	Pneumothorax (10035759)					

HBV Group= Subjects who previously received 4 doses of Infanrix hexa in first two years of life and received a challenge dose of HBV vaccine in this study

At least one symptom = at least one symptom experienced (regardless of the MedDRA Preferred Term)

N = number of subjects with the administered dose

n* = number of events reported

n/%,= number/percentage of subjects reporting the symptom at least once

95% CI = exact 95% confidence interval; LL = Lower Limit, UL = Upper Limit

Template 27 Number of subjects by country

	HBV Group N = xxx
Country	N
Xxxxx	
Xxxxx	
Xxx	

HBV Group= Subjects who previously received 4 doses of Infanrix hexa in first two years of life and received a challenge dose of HBV vaccine in this study

N = number of subjects

n= number of enrolled subjects included in each group

Template 28 Number of enrolled subjects by age category

Characteristics	Categories	HBV Group N =
Age category	n	
In utero		
Preterm newborn infants (gestational age < 37 wks)		
Newborns (0-27 days)		
Infants and toddlers (28 days-23 months)		
Children (2-11 years)		
Adolescents (12-17 years)		
Adults (18-64 years)		
From 65-84 years		
85 years and over		
Missing		

HBV Group= Subjects who previously received 4 doses of Infanrix hexa in first two years of life and received a challenge dose of HBV vaccine in this study

N = Number of enrolled subjects

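### SAP 11.2.6 counts subjects who did not report solicited symptoms as symptom-free, against SAP 11.2.5 and protocol 10.5

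*SAP*

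**What the plan says.** SAP 11.2.6 (Management of missing data) gives one rule for all reactogenicity and safety data: "Subjects who missed reporting symptoms (solicited/unsolicited or concomitant medications) will be treated as subjects without symptoms". The end of that sentence repeats the list and pairs each type of data with itself, so solicited symptoms are named deliberately.

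SAP 11.2.5 gives a different rule for solicited symptoms. Missing values are not replaced, and "the analyses of the solicited symptoms based on the TVC will include only subjects with documented safety data (i.e. symptom screen completed"). Its denominator table repeats this for each symptom group. For local symptoms, N is "All subjects with at least one solicited local symptom documented as either present or absent (i.e., symptom screen completed"), and the row for general symptoms is parallel.

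Protocol 10.5 carries the same rule as 11.2.5: "For the analyses of solicited symptoms, missing or non-evaluable measurements will not be replaced". Both sections let a missing report count as no event only for unsolicited adverse events and concomitant medication.

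The change that SAP section 9 lists for adverse events concerns presentation: "All the analysis of solicited and/or unsolicited adverse events will be performed for any, grade 3, by relationship to vaccination, and requiring medical attention". It says nothing about missing solicited data.

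In Annex 3, Templates 18 and 19 (solicited local and general symptoms) define "N = number of subjects with documented dose". Template 17 (solicited and unsolicited combined, Days 0-3) defines "N = number of subjects with administered dose", and Template 26 (combined, Days 0-30) defines "N = number of subjects with the administered dose".

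**The concern.** Adjacent SAP sections treat a subject with no symptom screen in opposite ways. Under 11.2.5 the subject leaves both numerator and denominator. Under 11.2.6 the subject stays in the denominator as free of every solicited symptom. Two programmers, each following one section, would produce different N, percentages and exact confidence intervals.

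The error would run in one direction only. Scoring unknown outcomes as absent can lower the reported reactogenicity but never raise it, and the interval would rest partly on subjects who supplied no data. Reactogenicity of the challenge dose is a secondary objective, and the SAP analyses the solicited symptoms with exact 95% intervals. If 11.2.6 were the rule used, the analysis would also depart from protocol 10.5 without being declared in SAP section 9.

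**Working it through.** **Step 1. Compare the rules by type of data.**

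| Data | Protocol 10.5 | SAP 11.2.5 | SAP 11.2.6 |
|---|---|---|---|
| Solicited, no completed screen | excluded | excluded | counted as no symptom |
| Unsolicited adverse events, no report | no event | no event | no event |
| Concomitant medication, no report | none taken | none taken | none taken |

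The conflict is confined to the first row.

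**Step 2. Inputs.** The plan states no figure to reproduce, since it gives neither an expected diary return nor an expected symptom rate. Planned enrolment is about 300 (protocol 4.1), and all are taken as vaccinated. A 40% symptom rate among completed screens is an assumption. So is the return of 90-99%. The 10% non-evaluable share in protocol 10.3 concerns the primary endpoint and is not a diary-return rate.

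**Step 3. Formula.** Let V be the number vaccinated, c the number of completed screens and x the number with the symptom.

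- 11.2.5: p = x/c
- Literal 11.2.6: p' = x/V = (x/c) × (c/V) = p × return share

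The shift is p × (1 − return share), which is zero or downward.

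**Step 4. Results** for V = 300 and p = 40%, with Clopper-Pearson 95% intervals where whole counts apply:

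| Return | 11.2.5 | Literal 11.2.6 | Shift (points) |
|---|---|---|---|
| 99% | 40.0% | 0.40 × 0.99 = 39.6% | 0.4 |
| 98% | 40.0% | 0.40 × 0.98 = 39.2% | 0.8 |
| 95% | 114/285 = 40.0% (34.3-45.9) | 114/300 = 38.0% (32.5-43.8) | 2.0 |
| 90% | 108/270 = 40.0% (34.1-46.1) | 108/300 = 36.0% (30.6-41.7) | 4.0 |

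**Step 5. Sensitivity to the symptom rate.** At 90% return, a 10% rate becomes 27/300 = 9.0% (shift 1.0 point) and a 70% rate becomes 189/300 = 63.0% (shift 7.0 points). At 99% return the shifts are 0.1 and 0.7 points.

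**Step 6. Blank items.** Suppose 285 local screens have at least one item documented, redness is blank on 6 of them, and 112 record redness. The 11.2.5 table keeps all 285 in N, so the percentage is 112/285 = 39.3%. Removing the blanks would give 112/279 = 40.1%. The table fixes N, but 11.2.5 does not say how the blank counts in n.

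**The case against.** The case for leaving this alone is substantial. Protocol 10.5, the text of SAP 11.2.5 and its denominator table all oppose one general line. Annex 3 points the same way: Templates 18 and 19 speak of a *documented* dose where Template 17 speaks of an *administered* dose, and the contrast has little purpose unless the first refers to completed screens. Protocol 5.6.12 has unreturned diary cards sought by telephone or other means, so the return may be high. Template 16 will report compliance, from which a reader could rescale the percentages. Every analysis is descriptive.

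There is also a narrower reading of 11.2.6: the 11.2.5 table sets N, and 11.2.6 only says that a blank item on a partly completed screen does not count in n. For blank items that gives the same count as the fix below.

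Most of this stands. It limits the size, and it shows that 11.2.6 should be brought into line with 11.2.5. It does not remove the contradiction. The sentence is about subjects who missed reporting, with no restriction to partly completed screens, and nothing ranks 11.2.5 above it. Template 16 helps a reader rescale only if the reader knows which rule produced the percentages.

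A reader might infer more in three places, and the documents do not support it.

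- *The templates leave the rule open.* The contrast in wording favours 11.2.5.
- *Templates 17 and 26 are wrong.* They include unsolicited events, for which all vaccinated subjects are the stated denominator, so N based on the administered dose is a defensible choice.
- *The 5% listing threshold of Template 26 is at risk.* Its N is the administered dose both before and after the fix, so no listing changes.

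**Conclusion.** The contradiction is definite and rests on the text alone. For solicited symptoms, SAP 11.2.6 conflicts with SAP 11.2.5 and protocol 10.5, and SAP section 9 does not list the difference.

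Its practical weight is small. Under the stated assumptions the understatement is 0.4 to 0.8 points at 98-99% return, within an interval about 11 to 12 points wide. It reaches 2 points at 95% return and 4 points at 90%, and it scales with the symptom rate. Active retrieval of diary cards makes the lower end more plausible, but the documents give no rate to confirm this.

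Only the solicited-symptom percentages and their intervals are affected. The primary endpoint, the sample size, unsolicited adverse events and concomitant medication are not. A reader might also infer that the SAP has already departed from the protocol. The documents show only conflicting instructions, and there would be a departure only if 11.2.6 were the rule applied.

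**What to change.** 1. Reword SAP 11.2.6 so that no report means no event for unsolicited adverse events and concomitant medication only. For solicited symptoms, exclude subjects without a completed screen and take N from the 11.2.5 table.
2. State the blank-item rule in the same place: where at least one local (or general) item is documented, the subject stays in N for that symptom group, and a blank item is not counted in n.
3. In Templates 18 and 19, replace the *documented dose* footnote with the 11.2.5 denominator wording.
4. Templates 17 and 26 may keep N as the administered dose, with a footnote giving the number of subjects without a completed screen.

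If the sponsor does intend non-reporters of solicited symptoms to count as symptom-free, 11.2.5 must be changed to match, and SAP section 9 must list the departure from protocol 10.5 with a reason.

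The cost is one reworded paragraph and footnotes on four templates. No new data are needed.

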11.2.7. Number of decimals displayed

The following decimal description from the decision rules will be used for the demography, immunogenicity and safety/reactogenicity.

Display Table	Parameters	Number of decimal digits
Demographic characteristics	Mean, median age	1
Demographic characteristics	SD (age)	1
Immunogenicity	Anti-HBs GMC, including LL & UL of CI	1
All summaries	% of count, including LL & UL of CI	1

12. ANNEX 2: SUMMARY ON ELIMINATION CODES

Refer to Section 5.2.

13. ANNEX 3: STUDY SPECIFIC MOCK TFL

The following draft study specific mock TFLs will be used.

The data display, title and footnote are for illustration purpose and will be adapted to the study specificity as indicated in the TFL TOC.

These templates were copied from DTPa-HBV-IPV-114 (106793) and additional tables required for public disclosure were added. Note that there may be few changes between the study specific SAP mock TFL and the final TFLs. These editorial/minor changes will not lead to a SAP amendment.

Template 1 Minimum and maximum activity dates (Total vaccinated cohort)

Activity number	Activity Description	Minimum date	Maximum date
10	VISIT 1		
20	VISIT 2		

Template 2 Number of subjects by center (Total vaccinated cohort)

Center PPD	HBV Group	
	n	%
...		
...		
All		

HBV Group= Subjects who previously received 4 doses of Infanrix hexa in first two years of life and received a challenge dose of HBV vaccine in this study

n = number of subjects included in each group or in total for a given center or for all centers

All = sum of all subjects in each group or in total (sum of all groups)

% = n/All x 100

Center = GSK Biologicals' assigned center number

Template 3 Number of subjects vaccinated, completed and withdrawn with reason for withdrawal (Total vaccinated cohort)

	HBV Group
Number of subjects vaccinated	
Number of subjects completed	
Number of subjects withdrawn	
Reasons for withdrawal :	
Serious Adverse Event	
Non-Serious Adverse Event	
Protocol violation	
Consent withdrawal (not due to an adverse event)	
Migrated/moved from study area	
Lost to follow-up (subjects with incomplete vaccination course)	
Lost to follow-up (subjects with complete vaccination course)	
Sponsor study termination	
Other	

HBV Group= Subjects who previously received 4 doses of Infanrix hexa in first two years of life and received a challenge dose of HBV vaccine in this study

Vaccinated = number of subjects who were vaccinated in the study

Completed = number of subjects who completed last study visit

Withdrawn = number of subjects who did not come back for the last visit

Template 4 Number of subjects at each visit and list of withdrawn subjects (Total vaccinated cohort)

Group	VISIT	N	Withdrawn Subject numbers	Reason for withdrawal
HBV Group	VISIT 1			
	VISIT 2			

HBV Group= Subjects who previously received 4 doses of Infanrix hexa in first two years of life and received a challenge dose of HBV vaccine in this study

N = Number of subjects who are still in the study up to the visit

Withdrawn = Subject who did not return after the visit

Template 5 Number of subjects enrolled into the study as well as the number of subjects excluded from ATP analyses with reasons for exclusion

Title	HBV Group		
	n	s	%
Total cohort			
Invalid informed consent or fraud data (code 900)			
Study vaccine dose not administered AT ALL but subject number allocated (code 1030)			
Total vaccinated cohort			
Administration of vaccine(s) forbidden in the protocol (code 1040)			
Study vaccine dose not administered according to protocol (code 1070)			
Non compliance with blood sampling schedule (including wrong and unknown dates (code 2090)			
Essential serological data missing (code 2100)			
Obvious incoherence or abnormality or error in data (code 2120)			
ATP cohort for analysis of immunogenicity			

HBV Group= Subjects who previously received 4 doses of Infanrix hexa in first two years of life and received a challenge dose of HBV vaccine in this study

Subjects may have more than one elimination code assigned therefore for each elimination reason n (s) is provided where:

n= number of subjects with the elimination code assigned excluding subjects who have been assigned a lower elimination code number

s= number of subjects with the elimination code assigned

% = percentage of subjects in the considered ATP cohort relative to the Total vaccinated cohort

Codes are listed based on a ranking order

Template 6 Deviations from specifications for age and intervals between study visits (Total vaccinated cohort)

Group	Age		VAC:1-SER:2
	Protocol	Protocol	
	from 14-15 Years	from 21 to 48 days	
HBV Group	N		
	n		
	%		
	range		

HBV Group= Subjects who previously received 4 doses of Infanrix hexa in first two years of life and received a challenge dose of HBV vaccine in this study

N = total number of subjects with available results

n/% = number / percentage of subjects with results outside of the interval

range = minimum-maximum for intervals

Age = Age computed at challenge dose

VAC: 1= Vaccination at visit 1

SER: 2= Blood sampling at visit 2

Template 7 Summary of demographic characteristics (Total vaccinated cohort)

		HBV Group N = XXX	
Characteristics	Parameters or Categories	Value or n	%
Age (Years) at challenge dose	Mean		
	SD		
	Median		
	Minimum		
	Maximum		
Gender	Female		
	Male		
Geographic Ancestry	African Heritage / African American		
	American Indian or Alaskan Native		
	Asian - Central / South Asian Heritage		
	Asian - East Asian Heritage		
	Asian - Japanese Heritage		
	Asian - South East Asian Heritage		
	Native Hawaiian or Other Pacific Islander		
	White - Arabic / North African Heritage		
	White - Caucasian / European Heritage		
	Other		

HBV Group= Subjects who previously received 4 doses of Infanrix hexa in first two years of life and received a challenge dose of HBV vaccine in this study

N = total number of subjects

n/% = number / percentage of subjects in a given category

Value = value of the considered parameter

SD = standard deviation

Template 8 Summary of vital signs characteristics (Total vaccinated cohort)

						HBV Group (N = xxx)			
Characteristics		Parameters			Value				
Height (cm)		Mean							
		SD							
		Median							
		Minimum							
		Maximum							
		Unknown							
Weight (kg)		Mean							
		SD							
		Median							
		Minimum							
		Maximum							
		Unknown							
BMI (kg/m ²)		Mean							
		SD							
		Median							
		Minimum							
		Maximum							
		Unknown							

HBV Group= Subjects who previously received 4 doses of Infanrix hexa in first two years of life and received a challenge dose of HBV vaccine in this study

N = total number of subjects

Value = value of the considered parameter

SD = standard deviation

Height (cm) = Height expressed in centimetres

Weight (kg) = Weight expressed in kilograms

BMI (kg/m²) = Body Mass Index in kilograms per meter square

Template 9 Percentage of subjects with antibody concentrations ≥ 6.2 mIU/mL, ≥ 10 mIU/mL, ≥ 100 mIU/mL and GMCs for anti-HBs antibody concentrations with 95% CI at pre-challenge dose and one month after the challenge dose (ATP cohort for analysis of immunogenicity)

Group	Timing	N	≥ 6.2 mIU/mL			≥ 10 mIU/mL			≥ 100 mIU/mL			GMC				
			n	%	95% CI		n	%	95% CI		n	%	95% CI		Value	95% CI
					LL	UL			LL	UL			LL	UL		
HBV Group	Pre															
	P1(D30)															

HBV Group= Subjects who previously received 4 doses of Infanrix hexa in first two years of life and received a challenge dose of HBV vaccine in this study

GMC = geometric mean antibody concentration calculated on all subjects

N = number of subjects with available results

[figure not shown]
n/% = number/percentage of subjects with concentration within the specified range

95% CI = 95% confidence interval; LL = Lower Limit, UL = Upper Limit

Pre: Blood sampling at pre-challenge dose time point

P1(D30): Blood sampling one month after the challenge dose

Template 10 Reverse cumulative distribution curve of anti-HBs antibody concentrations at <pre-challenge dose/one month after the challenge dose> (ATP cohort for analysis of immunogenicity)

HBV Group= Subjects who previously received 4 doses of Infanrix hexa in first two years of life and received a challenge dose of HBV vaccine in this study

Note: The groups shown in figure are indicative only. Actual groups may differ.

Template 11 Percentage of subjects with antibody concentrations ≥ 6.2 mIU/mL, ≥ 10 mIU/mL, ≥ 100 mIU/mL and GMCs for anti-HBs antibody concentrations stratified based on the pre-challenge dose status (ATP cohort for analysis of immunogenicity)

Group	Pre-vaccination status			≥ 6.2 mIU/mL		≥ 10 mIU/mL		≥ 100 mIU/mL		GMC				
		Timing	N	n	%	95% CI		95% CI		95% CI		value	LL	UL
						LL	UL	LL	UL	LL	UL			
HBV Group	< 6.2 mIU/mL	Pre												
		P1(D30)												
	≥ 6.2 mIU/mL - <10 mIU/mL	Pre												
		P1(D30)												
	≥ 10 mIU/mL	Pre												
		P1(D30)												
	Overall	Pre												
		P1(D30)												

HBV Group= Subjects who previously received 4 doses of Infanrix hexa in first two years of life and received a challenge dose of HBV vaccine in this study

GMC = geometric mean antibody concentration calculated on all subjects

N = number of subjects with available results

n/% = number/percentage of subjects with concentration within the specified range

95% CI = 95% confidence interval; LL = Lower Limit, UL = Upper Limit

Pre: Blood sampling at pre-challenge dose time point

P1(D30): Blood sampling one month after the challenge dose

Template 12 Anamnestic response for anti-HBs antibodies at one month after the challenge dose (ATP cohort for analysis of immunogenicity)

Group	Pre-vaccination status	Anamnestic response to the challenge dose				
				95% CI		
		N	n	%	LL	UL
HBV Group	S-					
	S+					
	Total					

HBV Group= Subjects who previously received 4 doses of Infanrix hexa in first two years of life and received a challenge dose of HBV vaccine in this study

S- = seronegative subjects (antibody concentration < 6.2mIU/mL for anti-HBs) prior to vaccination

S+ = seropositive subjects (antibody concentration \geq 6.2mIU/mL for anti-HBs) prior to vaccination

Total = subjects either seropositive or seronegative at pre-vaccination Challenge Dose response is defined as:

For initially seronegative subjects, antibody concentration greater than or equal to 10mIU/mL (\geq 10mIU/mL)

For initially seropositive subjects: antibody concentration at least four times the pre-challenge antibody concentration

N = number of subjects with both pre- and post-vaccination results available

n(%) = number(percentage) of responders

95% CI = exact 95% confidence interval; LL = lower limit, UL = upper limit

Template 13 Anamnestic response for anti-HBs antibodies at one month after the challenge dose stratified based on the pre-challenge dose status (ATP cohort for analysis of immunogenicity)

Group	Pre-vaccination status	Anamnestic response to the challenge dose				
				95% CI		
		N	n	%	LL	UL
HBV Group	< 6.2 mIU/mL					
	\geq 6.2 mIU/mL - <10 mIU/mL					
	\geq 10mIU/mL					
	Total					

HBV Group= Subjects who previously received 4 doses of Infanrix hexa in first two years of life and received a challenge dose of HBV vaccine in this study

S- = seronegative subjects (antibody concentration < 6.2mIU/mL for anti-HBs) prior to vaccination

S+ = seropositive subjects (antibody concentration \geq 6.2mIU/mL for anti-HBs) prior to vaccination

Total = subjects either seropositive or seronegative at pre-vaccination Challenge Dose response defined as:

For initially seronegative subjects, antibody concentration greater than or equal 10mIU/mL (\geq 10mIU/mL)

[figure not shown]
For initially seropositive: antibody concentration at least four times the pre-vaccination antibody concentration

N = number of subjects with both pre- and post-vaccination results available

n(%) = number(percentage) of responders

95% CI = exact 95% confidence interval; LL = lower limit, UL = upper limit

Template 14 Anti-HBs antibody concentrations post challenge as a function of pre-challenge concentrations, with regression line (ATP cohort for analysis of immunogenicity)

Regression equation and R^2 is given by

$$y = (a) + (b)x$$

$$R^2 = (c)$$

Where,

y= post challenge dose (log)

x= pre challenge dose (log)

R^2 = proportion of variation in post challenge dose (log) that is predictable from pre challenge dose (log)

$R^2 = (c)$ may be interpreted as follows: "(c) % of the variation in response variable is explained by regressors or regressors predict response variable by (c) %"

Template 15 Number and percentage of subjects who received study vaccine dose (Total vaccinated cohort)

		HBV Group N = XXX	
Total number of doses received	n	%	
1			

HBV Group= Subjects who previously received 4 doses of Infanrix hexa in first two years of life and received a challenge dose of HBV vaccine in this study

N = number of subjects in group included in the considered cohort

n/% = number/percentage of subjects receiving the specified total number of doses

Template 16 Compliance in returning symptom information (Total vaccinated cohort)

Group	Number of doses	Doses NOT according to protocol	Number of general SS	Compliance % general SS	Number of local SS	Compliance % local SS
HBV Group						

HBV Group= Subjects who previously received 4 doses of Infanrix hexa in first two years of life and received a challenge dose of HBV vaccine in this study

SS = Symptom screens/sheets used for the collection of local and general solicited AEs

Compliance % = (number of doses with symptom screen/sheet return / number of administered doses) X 100

Template 17 Percentage of subjects reporting either solicited symptoms or unsolicited adverse events during the 4-day (Days 0-3) post-vaccination period (Total vaccinated cohort)

Group	Any symptom			General symptoms			Local symptoms					
	N	N	%	95% CI	N	n	%	95% CI	N	n	%	95% CI
HBV Group												

HBV Group= Subjects who previously received 4 doses of Infanrix hexa in first two years of life and received a challenge dose of HBV vaccine in this study

N = number of subjects with administered dose

n/% = number/percentage of subjects presenting at least one type of symptom whatever the study vaccine administered

95%CI = Exact 95% confidence interval; LL = lower limit, UL = upper limit

Template 18 Percentage of subjects reporting solicited local symptoms during the 4-day (Days 0-3) post-vaccination period (Total vaccinated cohort)

Symptom	Type	HBV Group					95 % CI	
		N	n	%	LL	UL		
Pain	All							
	Grade 3							
	Medical advice							
Redness	All							
	> 50 mm							
	Medical advice							
Swelling	All							
	> 50 mm							
	Medical advice							

HBV Group= Subjects who previously received 4 doses of Infanrix hexa in first two years of life and received a challenge dose of HBV vaccine in this study

N = number of subjects with documented dose

n/% = number/percentage of subjects reporting the symptom at least once

95%CI = Exact 95% confidence interval; LL = lower limit, UL = upper limit

Grade 3 For Pain: severe: Significant pain at rest. Prevented normal everyday activities

For Redness/Swelling: > 50mm

Template 19 Percentage of subjects reporting solicited general symptoms during the 4-day (Days 0-3) post-vaccination period (Total vaccinated cohort)

Symptom	Type	HBV Group		95 % CI		
		N	n	%	LL	UL
Fatigue	All					
	Grade 3					
	Related					
	Medical advice					
Gastrointestinal symptoms	All					
	Grade 3					
	Related					
	Medical advice					
Headache	All					
	Grade 3					
	Related					
	Medical advice					
Temperature/(Oral) (°C)	All					
	≥37.5					
	>38.0					
	>38.5					
	>39.0					
	Related					
	>39.0 Related					
	Medical advice					

HBV Group= Subjects who previously received 4 doses of Infanrix hexa in first two years of life and received a challenge dose of HBV vaccine in this study

N = number of subjects with documented dose

n/% = number/percentage of subjects reporting the symptom at least once

95%CI = Exact 95% confidence interval; LL = lower limit, UL = upper limit

Grade 3 For Headache: Headache that prevented normal activity

For Temperature: > 39.0°C

For Fatigue: Fatigue that prevented normal activity

For Gastrointestinal symptoms: Gastrointestinal symptoms that prevented normal activity

Template 20 Percentage of subjects reporting the occurrence of unsolicited adverse events classified by MedDRA Primary System Organ Class and Preferred Term within the 31-day (Days 0-30) post-vaccination period (Total vaccinated cohort)

				HBV Group N = XXX	
				95% CI	
Primary System Organ Class (CODE)	Preferred Term (CODE)	n	%	LL	UL
At least one symptom					
Blood and lymphatic system disorders (10005329)	Leukocytosis (10024378)				
Cardiac disorders (10007541)	Angina unstable (10002388)				
	Mitral valve disease (10061532)				
	Myocardial infarction (10028596)				
Respiratory, thoracic and mediastinal disorders (10038738)	Pleural effusion (10035598)				
	Pneumothorax (10035759)				

HBV Group= Subjects who previously received 4 doses of Infanrix hexa in first two years of life and received a challenge dose of HBV vaccine in this study

At least one symptom = at least one symptom experienced (regardless of the MedDRA Preferred Term)

N = number of subjects with administered dose

n/% = number/percentage of subjects reporting the symptom at least once

95% CI = exact 95% confidence interval; LL = Lower Limit, UL = Upper Limit

Template 21 Number (%) of subjects reporting serious adverse events during the whole study period including number of events reported (Total vaccinated cohort)

Type of Event	Primary System Organ Class	Preferred Term (CODE)	Gr 1 N =			Gr2 N =		
			n*	n	%	n*	n	%
SAE	At least one symptom							
	<each SOC>	<each PT term>						
Related SAE	At least one symptom							
	<each SOC>	<each PT term>						
Fatal SAE	At least one symptom							
	<each SOC>	<each PT term>						
Related fatal SAE	At least one symptom							
	<each SOC>	<each PT term>						

HBV Group= Subjects who previously received 4 doses of Infanrix hexa in first two years of life and received a challenge dose of HBV vaccine in this study

At least one symptom = at least one symptom experienced (regardless of the MedDRA Preferred Term)

N = number of subjects with the administered dose

n* = number of events reported

n/% = number/percentage of subjects reporting the symptom at least once

Template 22 Number and percentage of subjects starting a concomitant medication during the 4-day (Days 0-3) post-vaccination period (Total vaccinated cohort)

	HBV Group					95% CI	
	N	n	%				
				LL	UL		
Any							
Any antipyretic							
Prophylactic antipyretic							

HBV Group= Subjects who previously received 4 doses of Infanrix hexa in first two years of life and received a challenge dose of HBV vaccine in this study

N = number of subjects with administered dose

n/% = number/percentage of subjects who started to take the specified concomitant medication at least once during the mentioned period

Template 23 Listing of SAEs (Total vaccinated cohort)

Group	Sub. No.	Age at onset (Year)	Sex	Verbatim	Preferred term	System Organ Class	MED type	Dose	Day of onset	Duration	Intensity	Causality	Outcome
HBV Group													

HBV Group= Subjects who previously received 4 doses of Infanrix hexa in first two years of life and received a challenge dose of HBV vaccine in this study

Template 24 Listing of dropouts from the study due to AEs, SAEs and solicited symptoms (Total vaccinated cohort)

Group	Study-Subject No.	Country	Gender	AE Description	SAE	Causality	Outcome	Type of discontinuation
HBV Group								

HBV Group= Subjects who previously received 4 doses of Infanrix hexa in first two years of life and received a challenge dose of HBV vaccine in this study

Template 25 Study population (Total vaccinated cohort)

Number of subjects	HBV Group
Planned, N	
Randomised, N (Total vaccinated cohort)	
Completed n (%)	
Demographics	HBV Group
N (Total vaccinated cohort)	
Females: Males	
Mean Age(At challenge dose), years (SD)	
Median Age, years (minimum, maximum)	
